### **6.3. Data Handling Procedures**

Only subjects included in the PK substudy analysis set and only samples obtained in this substudy will be included in the summary statistics for PK parameters. All analyses will be performed on data available at the time point considered. In summary tables, the number of subjects with missing data will be presented unless otherwise specified. In the calculation of percentages, subjects with missing data will not be considered in numerator or denominator unless otherwise specified.

#### **Missing Concentrations:**

Samples will be treated as missing for PK data analysis, if:

- Blood samples are collected but no bioanalytical data are reported;
- Missed PK sample collections;
- Samples are collected but the sampling time and/or dosing time are not recorded;
- Samples whose identities are uncertain due to possible handling or labelling errors conducted in the clinical site or bioanalytical labs;
- Sample is diluted and below the quantifiable limits.

#### **Protocol Deviations and/or Violations**

The data for subjects with significant protocol deviations and/or violations will be cautiously evaluated. If the deviation or violation has a significant impact on the filgotinib and its metabolite (GS-829845) PK profile, the data for those subjects should be excluded from the study's statistical evaluation by the pharmacokineticist and the reason for excluding individual data points will be recorded. Filgotinib and its metabolite (GS-829845) concentration data and PK parameters derived for those subjects will not be determined and reported.

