### Overall (Induction and Maintenance)

All safety data collected on or after the first dose of study drug administration for the entire study (Day 1) up to 30 days after permanent discontinuation of study drug will be summarized by treatment group according to the study drug received.

All data collected during the course of study will be included in data listings.

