### 8.7. Pharmacokinetic Analysis

For each individual study (Cohort A Induction Study, Cohort B Induction Study and Maintenance Study), plasma concentrations of filgotinib and its metabolite GS-829845 will be listed and summarized by treatment using descriptive statistics (eg, sample size, arithmetic mean, geometric mean, % coefficient of variation, standard deviation, median, minimum, and maximum). Plasma concentrations over time may also be plotted in semi-logarithmic and linear formats as mean  $\pm$  SD and median (Q1, Q3).

For subjects enrolled in the optional PK substudy, pharmacokinetic parameters of filgotinib and its metabolite GS-829845 will be listed and summarized by treatment; and plasma concentrations of the filgotinib and GS-829845 over time will be plotted in semi logarithmic and linear formats as mean  $\pm$  SD and median (Q1, Q3) by treatment.

Exposure-response relationships for efficacy and safety may also be evaluated.

CCI

[REDACTED]

CCI

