### **4.3. Protocol Deviations**

Subjects who did not meet the eligibility criteria for study entry, but enrolled in the study will be summarized. The summary will present the number and percentage of subjects who did not meet at least 1 eligibility criterion and the number of subjects who did not meet specific criteria by treatment group and overall based on the All Randomized Analysis Set. A by-subject listing will be provided for those subjects who did not meet at least 1 eligibility (inclusion or exclusion) criterion. The listing will present the eligibility criterion (or criteria if more than 1 deviation) that subjects did not meet and related comments, if collected.

Protocol deviations occurring after subjects entered the study are documented during routine monitoring. The number and percentage of subjects with major protocol deviations by deviation reason (eg, nonadherence to study drug, violation of key inclusion/exclusion criteria) will be summarized by treatment group and overall for the All Randomized Analysis Set for each individual study. A by-subject listing will be provided for those subjects with any major protocol deviation.

Similar summary and listing will be provided for major protocol deviations due to COVID-19.

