**6.4. Statistical Evaluations of PK Parameters**

For each individual study (Cohort A Induction Study, Cohort B Induction Study and Maintenance Study), plasma concentrations of filgotinib and its metabolite GS-829845 will be listed and summarized by treatment using descriptive statistics (eg, sample size, arithmetic mean, geometric mean, % coefficient of variation, standard deviation, median, minimum, and maximum).

For the subjects at the substudy, individual concentrations and PK parameters of filgotinib and its metabolite GS-829845 will be listed. Mean concentrations and PK parameters of filgotinib and its metabolite GS-829845 will be summarized descriptively. Individual and mean concentration-time profiles will be presented on semi-logarithmic and linear formats as mean  $\pm$  SD and median (Q1, Q3) by treatment.

For descriptive statistics of pharmacokinetic parameters and concentration data, sample size, arithmetic mean, geometric mean, % coefficient of variation, standard deviation, median, 1st quartile [Q1] (for concentration data only), 3rd quartile [Q3] (for concentration data only), minimum, and maximum, will be given.

Plasma concentrations for the subjects at each individual study and substudy will be listed by subject and nominal sampling time and summarized by nominal sampling time and treatment using descriptive statistics. Similarly, calculated plasma PK parameters for substudy will be listed by subject and summarized by treatment using descriptive statistics.

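### PKAP 6.3 withholds the concentrations of subjects excluded for a deviation, against the listing rules in protocol 8.7 and PKAP 6.4, and its exclusion trigger can depend on the measured result

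*SAP*

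**What the plan says.** PKAP 6.3, in its paragraph on protocol deviations and violations, applies to subjects with significant deviations. The condition for exclusion is: "If the deviation or violation has a significant impact on the filgotinib and its metabolite (GS-829845) PK profile". Such data are to be "excluded from the study's statistical evaluation by the pharmacokineticist", and "the reason for excluding individual data points will be recorded". The paragraph ends: "Filgotinib and its metabolite (GS-829845) concentration data and PK parameters derived for those subjects will not be determined and reported". It gives no threshold for a significant impact, no list of qualifying deviations, and no statement of whether the decision comes before or after concentrations are available.

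Four other places bear on this:

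- Protocol 8.7 says that, for each of the three studies, "plasma concentrations of filgotinib and its metabolite GS-829845 will be listed and summarized by treatment using descriptive statistics". It also lists the substudy parameters.
- PKAP 6.4 says that, for substudy subjects, "individual concentrations and PK parameters of filgotinib and its metabolite GS-829845 will be listed".
- SAP Section 3 promises by-subject listings for everyone in the All Randomized Analysis Set.
- PKAP Section 7 plans a table of subjects not included in the PK analysis. Its columns are subject, treatment, dose level and comments.

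**The concern.** Two separate things look wrong.

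The first is reporting. Leaving a subject out of a mean is one decision, and leaving that subject's measured values out of the report is another. PKAP 6.3 does both. A reader of the study report would see that someone was excluded and why, but could not judge whether the exclusion was reasonable or how far it moved the summary.

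The second is the trigger. A deviation leads to exclusion only if it affected the PK profile, and the PK profile is what the tables summarise. If that judgment is made on the measured values, subjects are kept or dropped according to their results. Summaries built that way can shift or look less variable than the data were. PK is a declared secondary endpoint in all three studies, and protocol 8.7 leaves room for exposure-response work on the same data.

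**Working it through.** The plan gives no figure on this point, so the check is mainly a comparison of text.

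**1. Reporting.** Protocol 8.7 and PKAP 6.4 list concentrations with no exception for deviations. PKAP 6.3 says the excluded subjects' concentrations will not be reported. All three cannot be followed for the same subject. Protocol 6.4.4 also says that filgotinib and metabolite concentrations will be analysed, so not determining them is a further departure.

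**2. Scope.** PKAP 6.3 opens by limiting the parameter summaries to the substudy, but the deviation paragraph does not repeat that limit. If it also reaches the sparse samples, it conflicts with protocol 8.2.1.3.2 as well, where one non-missing concentration is enough to enter the PK Analysis Set. The paragraph also mixes units: it excludes subjects but records reasons for individual data points.

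**3. Circularity.** There are two readings of how impact is judged.

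- From the measured profile: the concentrations must have been determined, so the closing sentence cannot be carried out as written, and the exclusion is selected on the result.
- From the nature of the deviation alone: there is no circularity and no selection on values. The qualifying deviations could then have been named in advance, and they are not.

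The text permits either reading. The reporting conflict in step 1 remains under both.

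**4. Comparison with the neighbouring rule.** The vomiting rule in the same section names an event and a time limit (at or before 2 times the median Tmax), and it excludes only from the statistical analysis. It does not withhold the data. The deviation rule has neither feature.

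**5. Illustration of the trigger.** This simulation takes the PKAP's approximate 16 subjects per dose. Everything else is assumed: log-normal AUC with a CV of 30%, 50% or 80%, and 2 or 4 deviating subjects whose deviation has no true PK effect. Each case used 100,000 repetitions. The last column compares the average log-scale SD with that of all 16 subjects.

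| Rule applied to deviating subjects | Geometric mean, ratio to truth | Log-scale SD, ratio to all 16 |
|---|---|---|
| Drop if more than 1 SD low | 1.009 to 1.045 | 0.984 to 0.965 |
| Drop if more than 1 SD off, either side | 1.00 | 0.967 to 0.930 |
| Drop all, regardless of value | 1.00 | not computed |

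So in this setting, exclusion that looks at the values can move the geometric mean by about 1% to 4.5% if it is one-sided, or not at all if it is two-sided. Either way it shrinks the apparent spread, by about 2% to 7%. Exclusion by deviation type alone leaves the geometric mean unbiased. The documents give no CV, no deviation rate and no cutoff, so these are illustrations and not estimates for this trial.

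**The case against.** The strongest reply is that the paragraph never says exclusion is decided after the concentrations are seen. The gate is a significant deviation, and its impact could be judged from what happened, such as a dose not taken. This stands: selection on the result is permitted by the wording, not prescribed by it.

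Protocol 8.2.1.3.1 also limits the substudy set to data that give interpretable results for the parameter concerned, so some exclusion from parameter summaries is already foreseen. This stands too, and the conflict does not lie in every exclusion. There is also partial disclosure. The reason is recorded, the PKAP tabulates the excluded subjects, and SAP 4.3 lists everyone with a major deviation. What is missing is the values.

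A reader might infer more than the documents support:

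- **That the rule mainly removes low-exposure subjects, so Cmax and AUC0-tau are overstated and CLss/F understated.** SAP 4.3 does give "nonadherence to study drug, violation of key inclusion/exclusion criteria" as examples of major deviations, and protocol Table 5-1 says strong P-gp inducers may lower exposure. But the substudy dose is taken under supervision in the clinic. Earlier missed doses could still matter, because the predose value stands in for the 24-hour point in AUC0-tau. Extra doses, wrong kits or mistimed samples could move exposure either way. No frequency is given for any of these.
- **That the effect is large.** If excluded subjects had 30% of typical exposure, dropping 1, 2 or 3 of 16 would multiply the geometric mean by 0.3^(-1/16) = 1.078, 0.3^(-2/16) = 1.162 or 0.3^(-3/16) = 1.253, which is 8% to 25%. The 30% and the counts are both invented. If such a subject had simply not taken the drug, leaving them out of a summary of filgotinib PK would not be a bias anyway.
- **That the protocol sentence "All data collected during the course of study will be included in data listings" settles the matter.** It closes Section 8.6, on safety, so it is supporting context at most. Protocol 8.7 is the firmer basis.

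**Conclusion.** The concern holds in a limited form. PKAP 6.3 contradicts protocol 8.7 and PKAP 6.4 by withholding the concentrations and parameters of subjects excluded for a deviation. That rests on the text alone and on no assumption. The paragraph is also circular if impact is judged from the profile.

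The trigger leaves room for exclusion to depend on the observed values, because it refers to the quantity being summarised and sets no threshold, list or timing. Whether that would happen, in which direction and by how much cannot be determined from the documents.

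PK is a descriptive secondary endpoint with no hypothesis test, so the multiplicity-controlled efficacy comparisons are untouched. The point is worth correcting because the correction is cheap and removes both the contradiction and the room for result-driven exclusion. It does not threaten the trial's main conclusions.

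**What to change.** In PKAP 6.3:

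1. Delete the last sentence of the paragraph on protocol deviations.
2. State that every measured concentration and every derivable parameter will be listed, with an exclusion flag and the reason. The shells for Listings 16.4.1 and 16.4.2 cover the substudy only, so the listing that carries the sparse samples needs the same flag.
3. Name the deviation types that lead to exclusion from summaries, and fix them before concentrations are released, without reference to the measured values. Say whether the rule applies to subjects or to single samples, and whether it covers the sparse samples as well as the substudy.
4. Keep the protocol's allowance for uninterpretable substudy profiles, as an exclusion from parameter summaries only.
5. Show Tables 14.4.2.x with and without the flagged subjects.

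The cost is PKAP wording, one flag column and one repeated set of parameter tables. No new data are needed.

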#### **Below the Lower Limit of Quantification Limit (BLQ)**

PK concentration values and PK parameter values below the lower limit of quantitation (BLQ) will be presented as "BLQ" in the data listings. BLQ values will be treated as 1/2 of the lower limit of quantitation (LLOQ) for calculation of geometric mean and CV%, and will be treated as 0 for all other summary statistics. Unexpected BLQ samples or samples whose identity is

uncertain due to possible handling or labeling errors can be treated as missing at the judgment of the pharmacokineticist and noted accordingly.

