### 8.3. Data Handling Conventions

Values for missing safety laboratory data will not be imputed. However, a missing baseline result will be replaced with a screening result, if available. If no pre-treatment laboratory value is available, the baseline value will be assumed to be normal (ie, no grade [Grade 0]) for the summary of graded laboratory abnormalities. If safety laboratory results for a subject are missing for any reason at a time point, the subject will be excluded from the calculation of summary statistics for that time point.

Values for missing vital signs data will not be imputed. However, a missing baseline result will be replaced with a screening result, if available.

PK concentration values and PK parameter values below the limit of quantitation (BLQ) will be presented as "BLQ" in the data listings. BLQ values that occur prior to the first dose will be treated as 0, BLQ values at all other time points will be treated as 1/2 of the lower limit of quantitation (LLOQ).

Laboratory data that are continuous in nature but are less than the LLOQ or above the upper limit of quantitation will be imputed to the value of the lower or upper limit minus or plus one significant digit, respectively (eg, if the result of a continuous laboratory test is  $< 20$ , a value of 19 will be assigned; if the result of a continuous laboratory test is  $< 20.0$ , a value of 19.9 will be assigned).

Procedures for handling missing data for CDAI, PRO2 and SES-CD (and components) will be described in the statistical analysis plan (SAP).

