Natural logarithm transformation will be used for plasma concentrations and analysis of PK parameters. Plasma concentration values that are below the limit of quantitation (BLQ) will be presented as “BLQ” in the concentration data listing. Values that are BLQ will be treated as 0 at predose time points, and one-half the value of the LOQ at postbaseline time points.

The following conventions will be used for the presentation of summary and order statistics:

- If at least 1 subject has a concentration value of BLQ for the time point, the minimum value will be displayed as “BLQ.”
- If more than 25% of the subjects have a concentration data value of BLQ for a given time point, the minimum and Q1 values will be displayed as “BLQ.”
- If more than 50% of the subjects have a concentration data value of BLQ for a given time point, the minimum, Q1, and median values will be displayed as “BLQ.”
- If more than 75% of the subjects have a concentration data value of BLQ for a given time point, the minimum, Q1, median, and Q3 values will be displayed as “BLQ.”
- If all subjects have concentration data values of BLQ for a given time point, all order statistics (minimum, Q1, median, Q3, and maximum) will be displayed as “BLQ.”

Pharmacokinetic parameters that are BLQ will be imputed as one-half LOQ before log transformation or statistical model fitting.

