**Table 14.4.2. Descriptive Statistics of Plasma Filgotinib and Metabolite GS-829845 Pharmacokinetic Parameters**

**Table 14.4.2.1. Descriptive Statistics of Plasma Pharmacokinetic Parameters of Filgotinib Following Once Daily Oral Administration of 200 mg Filgotinib at One Visit Between Week 2 and Week 10 in Subjects with Moderately to Severely Active Crohn's Disease**

Subject	Cmax (ng/mL)	Tmax (h)	Ctau (ng/mL)	AUC0-tau (ng*h/mL)	CLss/F (L/h)
N					
AM					
SD					
Min					
Median					
Max					
CV%					
GM					

AM: Arithmetic Mean; SD: Standard Deviation; Min: Minimum; Max: Maximum; GM: Geometric Mean; CV%: Arithmetic CV which is equal to SD/AM\*100.  
 Note: To estimate AUC0-tau, the concentration of 24h post-dose is based on imputed predose value.

**Table 14.4.2.2. Descriptive Statistics of Plasma Pharmacokinetic Parameters of Filgotinib Following Once Daily Oral Administration of 100 mg Filgotinib at One Visit Between Week 2 and Week 10 in Subjects with Moderately to Severely Active Crohn’s Disease**

**Table 14.4.2.3. Descriptive Statistics of Plasma Pharmacokinetic Parameters of GS-829845 Following Once Daily Oral Administration of 200 mg Filgotinib at One Visit Between Week 2 and Week 10 in Subjects with Moderately to Severely Active Crohn’s Disease**

Subject	Cmax (ng/mL)	Tmax (h)	Ctau (ng/mL)	AUC0-tau (ng*h/mL)	MRcmax	MRctau	MRAuctau
N							
AM							
SD							
Min							
Median							
Max							
CV%							
GM							

AM: Arithmetic Mean; SD: Standard Deviation; Min: Minimum; Max: Maximum; GM: Geometric Mean; CV%: Arithmetic CV which is equal to  $SD/AM*100$ .

Note: To estimate AUC0-tau, the concentration of 24h post-dose is based on imputed predose value.

MRcmax: Metabolic ratio of GS-829845 Cmax / filgotinib Cmax \* (425.51/357.43)

MRctau: Metabolic ratio of GS-829845 Ctau / filgotinib Ctau \* (425.51/357.43)

MRAuctau: Metabolic ratio of GS-829845 AUC0-tau / filgotinib AUC0-tau \* (425.51/357.43)

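### Three different BLQ rules for on-treatment PK troughs, one of which prints a CV% that does not match the mean and SD in the same table

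*SAP*

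**What the plan says.** - **Protocol 8.3, Data Handling Conventions:** "BLQ values that occur prior to the first dose will be treated as 0". At every other time point the substitute is half the LLOQ.
- **SAP 3.7, Data Handling Conventions and Transformations:** "Values that are BLQ will be treated as 0 at predose time points, and one-half the value of the LOQ at postbaseline time points". The same section states "Natural logarithm transformation will be used for plasma concentrations and analysis of PK parameters", and for derived parameters "Pharmacokinetic parameters that are BLQ will be imputed as one-half LOQ before log transformation or statistical model fitting".
- **PKAP 6.3, BLQ paragraph:** "BLQ values will be treated as 1/2 of the lower limit of quantitation (LLOQ) for calculation of geometric mean and CV"%. The sentence goes on to set zero for all remaining summary statistics. It makes no distinction by time point.
- **PKAP table footnotes (Tables 14.4.1 and 14.4.2):** CV% is the "Arithmetic CV which is equal to" SD/AM × 100. The same tables print AM, SD, CV% and GM.

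SAP Section 8 refers the PK analyses to the PKAP. SAP 3.7 nevertheless keeps its own rule, and no text says which of the three governs.

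**The concern.** PK characteristics of filgotinib and GS-829845 are the named other secondary endpoint of both induction studies and the maintenance study. Their presentation is descriptive, so the substitution rule directly determines the printed numbers. If the documents disagree on what a BLQ trough becomes, the same data give different means, SDs and CVs depending on which one the programmer follows.

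Two features need attention. The SAP's zero, if it applies to troughs, cannot be combined with a log transformation. The PKAP's use of two substitutes within one table produces rows that do not agree with each other.

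**Working it through.** **Step 1: which samples the rules apply to.** Protocol 6.4.4 and the Study Procedures Table (Protocol Appendix 2) place sparse PK sampling at Weeks 4, 10, 26 and 58, and the substudy profile at one visit from Week 2 to Week 10. The Week 10, Week 58 and first substudy samples are taken pre-dose; PKAP section 5 adds a pre-dose sample at Week 4. No PK sample is scheduled before the first dose of study drug, so every scheduled pre-dose sample is an on-treatment trough.

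**Step 2: apply each rule to a BLQ Week 10 trough.**

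| Document | AM, SD, median, minimum | GM, CV% |
|---|---|---|
| Protocol 8.3 | half LLOQ | half LLOQ |
| SAP 3.7, read as a predose sample | 0 | 0 (log undefined) |
| SAP 3.7, read as a postbaseline sample | half LOQ | half LOQ |
| PKAP 6.3 | 0 | half LLOQ |

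The sample is both predose and postbaseline, so both SAP clauses fit it. On the zero reading, one BLQ trough leaves the log concentration and the geometric mean undefined.

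**Step 3: direction of the PKAP mismatch.** Let n be the number of subjects, k of them BLQ (1 ≤ k < n), with common substitute c. Raising c from 0 to LLOQ/2 raises the mean. The sum of squares SS about the mean changes at rate dSS/dc = 2k(c − mean). This is negative because every quantifiable value exceeds c. So AM rises and SD falls, and the printed CV% (from half LLOQ) is always below 100 × printed SD / printed AM (from zeros).

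**Step 4: an example that can be checked by hand.** Assumed LLOQ 10; ten troughs, five BLQ, the others 12, 18, 25, 30 and 40.
- Zeros: AM = 125/10 = 12.5; SD = √[(3593 − 10 × 12.5²)/9] = √225.6 = 15.02; SD/AM × 100 = 120.2.
- Half LLOQ = 5: AM = 150/10 = 15.0; SD = √[(3718 − 10 × 15²)/9] = √163.1 = 12.77; CV% = 85.1.

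The PKAP table would print AM 12.5, SD 15.0 and CV% 85.1.

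**Step 5: range.** The documents give neither the LLOQ, the trough distribution nor the BLQ fraction. Assumptions, in LLOQ units: n = 16 (the PKAP's approximate substudy size per dose); k values BLQ; the rest at lognormal quantiles with log-SD 0.8, floored at 1 LLOQ, with nominal geometric mean 2, 5 or 20 LLOQ. Each cell shows printed CV% / SD/AM × 100 from the printed AM and SD (computed unrounded).

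| k of 16 BLQ | GM 2 LLOQ | GM 5 LLOQ | GM 20 LLOQ |
|---|---|---|---|
| 1 | 82.6 / 85.0 | 87.8 / 88.8 | 88.5 / 88.8 |
| 4 | 94.7 / 106.3 | 104.9 / 110.0 | 108.7 / 110.0 |
| 8 | 111.2 / 145.3 | 133.2 / 148.9 | 144.7 / 148.9 |
| 12 | 119.9 / 218.5 | 170.1 / 222.5 | 207.2 / 222.5 |

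With k = 12 and GM 2 LLOQ, the PKAP table would also print a geometric mean (0.72) above the arithmetic mean (0.63), which cannot happen within one set of positive numbers. If all 16 were BLQ it would print AM 0, SD 0, CV% 0 and GM 0.5, while SD/AM is 0/0.

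**The case against.** **The SAP can be read benignly.** SAP 3.7 sets predose against postbaseline, and SAP 3.8.1 defines baseline as on or before the first dosing date. On that reading Week 10 and Week 58 samples are postbaseline and take half the LOQ, as in the protocol. This stands as a possible reading, so the SAP does not unambiguously impose zero on troughs. But Protocol 6.4.4 calls those same samples pre-dose, and on the benign reading the SAP's zero clause has no scheduled sample to apply to. Both labels fit, and the text does not choose.

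**Precedence is partly settled.** SAP Section 8 points to the PKAP, and the SAP revision table says the PK description was replaced by it, so the rule in 3.7 may be left over. The PKAP plans only descriptive summaries and takes its geometric mean with half LLOQ, so nothing in the PKAP itself requires the log of zero. That is fair, but the SAP 3.7 rule remains in force as written, and the PKAP still departs from the protocol.

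**The footnote formula is not strictly violated.** SD/AM computed on half-LLOQ values does satisfy it. What remains is that this SD and AM are not the ones printed.

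**Two stronger readings are tempting, and the documents do not support them.**
- *That two of the rules fail for steady-state troughs.* The protocol and PKAP rules can both be computed for troughs. Only the SAP concentration rule breaks down, and only on its zero reading. The PKAP's defect is mixing substitutes, which is not specific to troughs.
- *That the metabolic ratio MRctau becomes undefined.* No text tells the analyst to divide by a zero Ctau. The PKAP confines zero to summary statistics, and SAP 3.7 imputes BLQ parameters at half the LOQ before log transformation or model fitting. At most, the PKAP omits to say what value a BLQ predose takes when parameters are derived.

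**Conclusion.** The point holds in a limited form. The three documents give different BLQ rules for on-treatment troughs. The SAP wording allows two values for the same sample, one of which is incompatible with its own log transformation. The PKAP's printed CV% will not equal SD/AM × 100 from the same table whenever a value is BLQ.

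The inconsistency follows from the text alone; its size does not. Under the stated assumptions the CV% gap runs from 0.3 points (88.5 vs 88.8) to 98.6 points (119.9 vs 218.5). It is small when quantifiable troughs lie well above the LLOQ and few are BLQ. The hand example (85.1 vs 120.2) is one case within that range and not an expected value.

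Only descriptive PK summaries are affected. Individual BLQ results are listed as BLQ under all three texts, and efficacy, alpha and sample size are untouched. This is a minor point.

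**What to change.** Put the protocol's rule into SAP 3.7 and PKAP 6.3: zero only for BLQ values before the first dose of study drug, and half the LLOQ at every later time point, with on-treatment troughs named explicitly. Compute AM, SD, CV% and geometric mean from that single set of substituted values. CV% then equals SD/AM × 100 by construction, and the geometric mean is defined and cannot exceed the arithmetic mean. For 4 of 16 BLQ and GM 2 LLOQ, the table would read AM 2.15, SD 2.04, CV% 94.7, GM 1.50 in LLOQ units.

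Two sentences are worth adding in the same edit: the value a BLQ predose takes when it enters Ctau and the 24-hour point of the AUC, and whether the SAP 3.7 convention of displaying low order statistics as BLQ applies to the PKAP tables.

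The cost is wording, with a matching setting in the PK summary programs. No sampling, data collection or efficacy analysis changes.
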